14.0 Potential Benefits to Participants

14.1 Potential Benefits:

There will be no personal or immediate benefit of participating for our subjects.

15.0 Statistical Considerations

15.1 Data Analysis Plan:

De-identified MRI and MRS data will be analyzed in a blind fashion at UMN, as described previously for volumetric, VBM (18, 45) and MRS (22, 43) analyses. Diffusion MRI data will be analyzed using tract-based spatial statistics (TBSS) (46), which is part of the FMRIB's Software Library (FSL (47)), and tractography to delineate particular WM pathways (e.g.,

cerebellar peduncles). Functional (rs fMRI data) will be pre-processed using FSL, followed by between-group analyses using seed-based connectivity analysis for particular regions of interest, and ICA/dual regression (MELODIC/FIX)) (48, 49) for RSNs. Outcome measures will consist of cerebellar and brainstem volumes, GM, and WM loss metrics from VBM, metabolite concentrations, FA, MD, RD and AD, as well as degree of co-activation within RSNs of interest (e.g., motor function).

15.2 Power Analysis:

The sample size calculation for this study is based on imaging data that will be acquired at 6 imaging sites, for a total sample size of 100 subjects, namely a 30 (20 premanifest and 10 early-phase) subjects with the SCA1 mutation, 40 (27 premanifest and 13 early-phase) subjects with the SCA3 mutation and 30 controls. The at-risk subject study by the EASG group, which included imaging data from 26 SCA1 mutation carriers and 9 SCA3 mutation carriers, reported significant VBM alterations in SCA1 and trends in SCA3 (18). Based on these data, a Wilcoxon rank sum test will have 95% power to show a difference between controls (mean = 0.018, SD = 0.019) and SCA (mean = 0.016, SD = 0.0019) with 30 subjects per group ($\alpha = 0.025$ to take into account the two comparisons of SCA1 and SCA3 versus controls, two-tailed test). Note that this power computation is conservative since the EASG study included only at-risk subjects, whereas the current study will include both premanifest and early manifest patients. In addition, based on our MRS preliminary data described above, a Wilcoxon-Mann-Whitney test will have 94% power to show a difference in NAA at baseline between premanifest subjects who have disease onset within the 5 years of the U01 (conservatively estimated at 1/3 of the patients i.e. $n=7$, mean = 1.2) and those patients who remain in the premanifest stage ($n=14$, mean = 2) for the SCA1 group (standard deviation of 0.4, $\alpha = 0.05$, two-tailed test). We will recruit a larger sample size for the SCA3 cohort because: 1) imaging alterations did not reach significance for SCA3 mutation carriers in the at-risk EASG study; 2) the diffusion MRI abnormalities in our preliminary data (see section 2.2) were less pronounced in SCA3 than those in SCA1; and 3) SCA3 is the most common SCA, enabling recruitment of a larger cohort.

15.3 Statistical Analysis:

To compare the imaging biomarkers between SCA1, SCA3 and control cohorts, globally and in a pairwise fashion, we will use Wilcoxon rank sum test. In addition, premanifest carriers and early-stage patients will be compared using Wilcoxon rank sum test. Within each SCA group, premanifest and manifest patients will be compared regarding the biomarkers at baseline and during follow-up. If this approach is not conclusive, cluster approaches will be carried out. Sex will be considered as a biological variable to assess potential sex-based differences in imaging results.

15.4 Data Integrity:

Non-biological sources of data variation due to MR hardware and software will be minimized by procedures for quality assurance (QA), which prospectively aims to avoid production of poor quality data, and retrospective quality control (QC) to identify poor quality data. All participating MR sites of the U01 project routinely verify scanner stability with regular QA tests on their 3T scanners, e.g. with a weekly American College of Radiology (ACR) phantom protocol. In addition, we will follow the guidelines put forth by the MRS Consensus Group for quality management in clinical MR spectroscopy (50), including regular MRS-specific tests with a dedicated phantom that has a composition of the most concentrated neurochemicals in the brain at appropriate proportions (GE MRS-HD-Sphere). The imaging sites of the U01 will be required to meet consistent performance metrics prior to subject accrual. QC criteria will be applied uniformly to all data prior to inclusion in final analyses. The assessment will be based on quantitative quality metrics (signal-to-noise ratio, contrast-to-noise ratio, identification of image and spectral artifacts and, in addition, for MRS, linewidth, % water suppression and Cramér-Rao lower bounds). To accomplish these QC procedures, all MRI and MRS data will be sent by U01 imaging sites to UMN monthly, using the data management software Flywheel (<https://flywheel.io/>).

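### The main power calculation prints a control SD of 0.019, ten times the SCA SD; with that input the claimed 95% power falls to about 8%

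*Protocol*

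**What the plan says.** Section 15.2 of the protocol introduces the sample-size calculation for a total of 100 subjects at six imaging sites: 30 with the SCA1 mutation, 40 with SCA3 and 30 controls. Drawing on voxel-based morphometry (VBM) data from an earlier European study of at-risk subjects, it states that "a Wilcoxon rank sum test will have 95% power to show a difference". The inputs follow in the same sentence: a "difference between controls (mean = 0.018, SD = 0.019) and SCA (mean = 0.016, SD = 0.0019) with 30 subjects per group". Alpha is set at 0.025 for the "two comparisons of SCA1 and SCA3 versus controls, two-tailed test".

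Section 15.3 then plans pairwise Wilcoxon rank sum tests between the SCA1, SCA3 and control cohorts. Section 15.2 contains one other power calculation, for NAA in 7 against 14 premanifest SCA1 subjects. That is a comparison within SCA1 and involves no controls.

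**The concern.** The two SDs differ by a factor of exactly ten (0.019 / 0.0019), and the control SD exceeds the control mean (0.019 against 0.018). The protocol neither explains a tenfold difference in spread nor gives the control SD anywhere else.

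The difference in means is 0.018 - 0.016 = 0.002. That is about one SD if the SD is 0.0019, and about a tenth of an SD if it is 0.019. The choice between the two values therefore decides whether 30 per group is ample or nearly useless. A reader who takes the sentence at face value cannot reproduce the claim. Anyone reusing these inputs to plan a later trial, which is the purpose of a trial-readiness study, could carry forward a control SD ten times too large.

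**Working it through.** **Inputs, all from section 15.2.** Control mean 0.018 and SD 0.019; SCA mean 0.016 and SD 0.0019; 30 per group; two-tailed alpha 0.025; Wilcoxon rank sum test; claimed power 95%.

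**Step 1: normal approximation with the printed SDs.**
- Standard error of the difference = sqrt((0.019² + 0.0019²)/30) = 0.00349.
- Standardised difference = 0.002 / 0.00349 = 0.574.
- Critical value for two-tailed alpha 0.025 = 2.241.
- Power ≈ Φ(0.574 - 2.241) = Φ(-1.668) = 4.8%.

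**Step 2: the same formula with 0.0019 in both groups.**
- Standard error = sqrt(2 × 0.0019²/30) = 0.000491.
- Standardised difference = 0.002 / 0.000491 = 4.077.
- Power ≈ Φ(4.077 - 2.241) = 96.7%.
- The rank sum test is slightly less efficient than this on normal data. A noncentral-t calculation with n multiplied by 0.955 gives 95.1%.

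**Step 3: simulation of the planned test.** Normal data, 40,000 runs per case, two-sided rank sum test with asymptotic p-value, alpha 0.025 unless noted:

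| Case | Rejection rate |
|---|---|
| SDs as printed (0.019 / 0.0019), 30 v 30 | 7.7% |
| SDs as printed, 30 controls v 40 SCA3 | 10.3% |
| SDs as printed, 30 v 30, alpha 0.05 | 12.4% |
| SDs as printed, 30 v 30, alpha 0.10 | 20.4% |
| SD 0.019 in both groups, 30 v 30 | 3.4% |
| SD 0.0019 in both groups, 30 v 30 | 94.9% |

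A Welch t-test in the same runs gives 4.7% for the first row. Only the last row reproduces the protocol's 95%.

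**Step 4: sample size needed for 95% power with the printed SDs.**
- Mean variance = (0.019² + 0.0019²)/2 = 0.01350².
- n per group = 2 × (2.241 + 1.645)² × 0.01350² / 0.002² ≈ 1,377, against the 30 planned.

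**Step 5: two side checks.**
- If controls were normal with mean 0.018 and SD 0.019, the share below zero would be Φ(-0.018/0.019) = Φ(-0.947), about 17%. That is odd for a morphometric measure.
- With equal means and the printed SDs, the rank sum test rejects in about 5% of runs at a nominal 2.5%. So part of the 8% is a response to unequal spread.

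**The case against.** The strongest reply is that this is a misprint in one digit and says nothing about the study's real power, which depends on the true SD. With 0.0019 in both groups the same n, alpha and test return the claimed 95%, and neither the 30 per group nor the total of 100 changes. This stands: the finding does not show that 30 per group is too few.

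The figure of 8% also rests on normal data. With the printed mean and SD but a non-negative control distribution, the rejection rate is about 25% (lognormal) or 20% (gamma). Almost all of those rejections go the wrong way, because the skewed control median lies below the SCA values. So 8% needs the qualifier of normal data; far below 95% does not. The negative-values argument is likewise only suggestive, since the protocol does not say which VBM metric the means describe. The point about the test's level matters only if 0.019 is real.

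The calculation is also not the sole support for all 100 subjects: the larger SCA3 group rests on three qualitative reasons, and there is the NAA calculation. It remains the only power calculation for SCA against controls.

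Finally, a zero might have been lost when the PDF was read. Nothing shows this, and the neighbouring 0.0019 came through intact. The same check against the source would settle it.

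**Conclusion.** The concern holds. As written, the inputs in section 15.2 contradict the stated result: about 8% power for the rank sum test under normal data, about 5% by a Welch t-test or normal approximation, against a claim of 95%. No variation of alpha, sidedness or group size examined with the printed SDs brings the figure near 95%.

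The most probable reading is that the control SD should be 0.0019, which reproduces the claim at 94.9%. That is an inference from the arithmetic; the source value is not in the protocol. If it is right, the error lies in the stated input and the sample size is sound on the plan's own assumptions. If 0.019 is the true control SD, the sample-size justification for the SCA-versus-control comparisons fails.

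**What to change.** Check the control SD in section 15.2 against the data it was taken from.

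- If it is 0.0019, print SD = 0.0019 for both groups and keep the 95% and the 30 per group.
- If it is 0.019, withdraw the 95% claim, recompute power for the planned test with the correct inputs, and reconsider the sample size. Allow for the rank sum test exceeding its nominal level when the spreads are this unequal.

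While the sentence is open, it would help to name the VBM metric and region the means describe, so that the inputs can be traced; this is a convenience and not part of the error. In the likely case the cost is a look at the source and a one-line protocol correction, with no change to design, recruitment or analysis.

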2.0 Background

2.1 Significance of Research Question/Purpose:

SCAs are hereditary movement disorders in which cerebellar neurodegeneration results in progressive balance and coordination deficits (1). They are disabling, fatal and cause significant physical, psychological, social and economic burdens to patients and caregivers. While they are currently untreatable, neuronal and motor dysfunction is reversible in SCA mouse models (2, 3). Furthermore, advances in understanding of molecular mechanisms of common SCAs (1, 4) have raised a realistic hope for the development of effective therapeutic interventions (5). For example, therapies based on gene silencing show great promise for the polyglutamine (CAG repeat expansion) disorders SCA1, 2, 3 and 6 (3, 6, 7). Therefore, the need for establishing imaging biomarkers to monitor cerebral pathology is more pressing than ever.

SCAs 1, 2, 3, and 6 are the most prevalent SCAs in the US (8) and Europe (9). Of these, SCA1 progresses more rapidly than SCA2, 3 and 6 (8, 9), allowing shorter clinical trials, and SCA3 is the most prevalent SCA worldwide (8-10), allowing the recruitment of a large number of patients into clinical trials. SCA1 and SCA3 are relentlessly progressive, disabling, and eventually fatal neurodegenerative diseases with no efficacious treatments other than supportive therapy (11, 12). Importantly, several clinical trials for disease modifying therapies in SCA1 and SCA3 are anticipated within the next 5 years. Most clinical trials, thus far, have included SCA patients at all stages of disease and phenotypes, and may therefore have missed a therapeutic window. Mounting evidence argues for administration of therapies in the earliest, including *premanifest*, stages of neurodegeneration. Namely, inducible genetic mouse models of polyQ diseases including SCA1 (2, 13-15) show disease reversibility early on, which is lost as the disease progresses, with increasing cellular dysfunction and cell death in the brain. Consistent with this, efficacy of a novel antisense oligonucleotide (ASO) treatment doubled when administered in the pre-symptomatic vs. symptomatic phase in another hereditary neurodegenerative disease (16, 17). Hence, in this project we will focus on premanifest gene carriers who have no ataxia (score on the Scale for the Assessment and

Rating of Ataxia [SARA] <3; maximum score = 40) (18, 19) and early-stage patients (SARA 3-9).

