This study will define characteristics of the earliest disease progression measurable by MRI and MRS, with a goal to predict disease onset in premanifest individuals based on a multi-parametric model that incorporates imaging biomarkers. While we do have an existing predictive model to estimate the future age at onset for the major SCAs based on CAG repeat size and current age (20) there is great variability in onset ages between patients with the same CAG repeat, even within the same family. Therefore, measuring cerebral disease onset by noninvasive imaging is bound to substantially improve the estimation of onset age of manifest disease and allow recruitment of those premanifest patients who are closest to disease onset into future trials. Despite wide utility of brain MR biomarkers in neurological disorders, an advanced, 1-hour, 3T morphometric, biochemical and functional imaging marker protocol has not been validated in a multi-site trial setting and is likely to serve as a template in future neurodegenerative disease trials.

This protocol application is for local MRI/MRS acquisition and centralized data analysis under a recently funded multi-site U01 grant (U01NS104326-01, contact PI: [name], Houston Methodist Research Institute; [name], MPI) for clinical trial readiness in SCA1 and SCA3. The Center for Magnetic Resonance Research (CMRR) is the lead imaging site for analysis of multi-site MRI data. Subjects will be identified by the Clinical Research Consortium for Studies of Cerebellar Ataxias (CRC-SCA) investigators, evaluated clinically and referred for MR scanning to select imaging sites. All imaging will be done under local IRB approval.

2.2 Preliminary Data:

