8.0 Study Population

8.1 Inclusion Criteria:

- 1.** Participants must be 18 years or older.
- 2.** Participants must understand and cooperate with requirements of the study in the opinion of the investigators and must be able to provide written informed consent.
- 3.** Individuals with ataxia and healthy volunteers who are medically stable for participation in study in the opinion of the investigators. [DNA testing will be performed for all individuals with ataxia and at-risk participants by the U01 team under a central IRB and is *not* included in this protocol]

8.2 Exclusion Criteria:

- 1.** Known genotype consistent with other inherited ataxias.
- 2.** Concomitant disorder(s) or condition(s) that affects assessment of ataxia or severity of ataxia during this study
- 3.** Investigational drugs taken 2 months prior to participation in this study
- 4.** Changes in coordinative physical and occupational therapy for ataxia 2 months prior to study participation
- 5.** Medical conditions likely to interfere with the study, including neurologic conditions other than ataxia, restless leg syndrome, structural abnormalities such as subdural hematoma, intracranial neoplasms, concurrent illnesses or treatments interfering with cognitive function such as dementia, stroke or normal pressure hydrocephalus. A SARA score above 2 will be exclusion criterion for healthy control participants.

6. Pregnant or lactating or those women of child-bearing age who are not using acceptable forms of contraception.
7. Inability to undergo MRI scanning, including but not limited to claustrophobia, unable to remain still in an MRI scanner for more than 30 minutes, presence of paramagnetic substances or pacemakers in body, weight over 300 lbs.
8. Inability to adhere to study protocol for whatever reason.

8.3 Screening:

Subjects will be screened clinically by the lead site of the U01 grant (Houston Methodist Research Institute) for disease stage under the central IRB for the U01 grant.

For MR safety screening, the research team will utilize the CMRR Center's screening tools and adhere to the screening SOP during enrollment of all research participants in this protocol. The CMRR Center's screening tools and SOP are IRB approved under the CMRR Center Grant (HSC# 1406M51205) and information regarding screening procedures is publicly available on the CMRR website ([CMRR Policies / Procedures](#)).

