11.0 Local Recruitment Methods

11.1 Recruitment Process:

Subjects will be recruited from the clinical practices of U01 site investigators, which in the US is comprised of sites of the Clinical Research Consortium for Studies of Cerebellar Ataxias (CRC-SCA), under central IRB for the U01 study. Patients will also be recruited to the U01 study by notices in ataxia newsletters, e.g. the NAF newsletter, and through flyers. In addition, patients who have previously participated in our ataxia study may be contacted by our study coordinator, as stated in the consent form they signed when they participated in our earlier ataxia studies (under protocol # 0502M67488). Control participants will be recruited through the CMRR volunteer mailing list or in person.

A phone screening interview will be conducted by the study coordinator for MR safety and other inclusion/exclusion criteria using the CMRR safety

screening form. A phone script for this purpose is attached in Supporting Documents.

11.2 Identification of Potential Participants:

Subjects will be identified from among the enrollees of the multi-site U01 clinical study (performed under a central IRB and *not* covered under the current IRB protocol), screened clinically by the lead site of the U01 grant (Houston Methodist Research Institute) for disease stage and referred to UMN for MR safety screening prior to enrollment.

In addition, the research team will utilize the CMRR Center's volunteer pool for recruitment of healthy research volunteers in this protocol. The CMRR Center's volunteer pool is IRB approved under the CMRR Center Grant (HSC# 1406M51205) and information regarding volunteers is publicly available on the CMRR website ([CMRR Policies / Procedures](#)). The control group will also likely include spouses and friends of patient participants who find out about the study through their relation with the patient.

11.3 Recruitment Materials:

Recruitment will be done by the multi-site U01 clinical study under a central IRB. In addition, healthy volunteers will be recruited through the CMRR Center's volunteer pool (IRB approved under the CMRR Center Grant, HSC# 1406M51205).

11.4 Payment:

Subjects will not be responsible for the cost of any study procedure. They will be compensated \$50 for each MRI scan visit. If they need to stop any testing for any reason, they will receive partial payment for their time.

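### Section 15.3 fixes a rank sum test that assumes independent subjects, although spouse controls are expected and several members of one family may be enrolled

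*Protocol*

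**What the plan says.** Section 15.3 is specific about the method. For the three cohorts it states: "To compare the imaging biomarkers between SCA1, SCA3 and control cohorts, globally and in a pairwise fashion, we will use Wilcoxon rank sum test". For disease stage it adds that "premanifest carriers and early-stage patients will be compared using Wilcoxon rank sum test". The only further device is a fallback: "If this approach is not conclusive, cluster approaches will be carried out". Neither 15.2 nor 15.3 mentions family, pairing or household.

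On who is enrolled:

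- Section 2.1 opens with "SCAs are hereditary movement disorders".
- Section 8.1 notes that "DNA testing will be performed for all individuals with ataxia and at-risk participants by the U01 team". No criterion in 8.1 or 8.2 limits enrolment to one member of a family.
- Section 11.1 takes carriers from the clinics of the U01 investigators, with newsletters, flyers and earlier participants as further routes.
- On controls, section 11.1 says "Control participants will be recruited through the CMRR volunteer mailing list or in person", and section 11.2 adds: "The control group will also likely include spouses and friends of patient participants".
- Section 16.1 describes one code per subject and mentions no family or household code.

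**The concern.** The null distribution of the ordinary Wilcoxon rank sum test requires all observations to be independent. A person at risk of a hereditary ataxia has an affected relative, and clinic-based recruitment makes it plausible that some of these relatives are enrolled too. Relatives share the mutation and part of their genetic background, and possibly the site and scanner, so their imaging markers may be positively correlated.

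The direction of the error depends on where the related subjects fall:

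- **Same group** (two SCA1 relatives in SCA1 v controls or SCA1 v SCA3): the group holds less information than its size suggests, and p-values come out too small. SCA1 v SCA3 is hit hardest because both groups can be clustered.
- **Opposite groups** (a premanifest and an early-stage member of one family, or a patient and a spouse control): part of the variation cancels in the contrast. The test does not use this, and p-values come out too large.

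The study exists to validate markers at the premanifest and early stages. Either error could change which markers are judged to separate the groups.

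**Working it through.** **Inputs from the protocol (15.2).** SCA1: 30 carriers (20 premanifest, 10 early-phase). SCA3: 40 carriers (27 and 13). Controls: 30. Pooled over genotype, this is 20 + 27 = 47 premanifest and 10 + 13 = 23 early-stage. The level is 0.025 two-sided for each SCA v control comparison. I use 0.05 for the other contrasts, which is an assumption.

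**Inputs not in the protocol (assumed).** Number and size of enrolled families, within-family correlation ρ, and number of patient-spouse pairs.

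**The plan's own figure.** The 95% power with 30 per group and a difference of 0.018 − 0.016 = 0.002 reproduces under independence at 94.8% by simulation, if the SD is 0.0019 in both groups. (The control SD is printed as 0.019, which would give about 8%. That is a separate matter.) The stated power thus takes all subjects as independent.

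**Formula.** Let R be the true variance of the difference in group means divided by the variance under independence. In large samples the actual level is about 2[1 − Φ(z/√R)], with z = 2.241 for nominal 2.5% and 1.960 for nominal 5%. With unit variance, a group of n containing k related pairs has its variance multiplied by D = 1 + 2kρ/n. If everyone is in a family of m, D = 1 + (m − 1)ρ.

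**Worked cases at ρ = 0.5**

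- SCA1 v independent controls, all in families of 2: D = 1.5, R = (1.5 + 1)/2 = 1.25, z/√R = 2.005, level 4.5% (simulated 4.4%).
- SCA1 v SCA3, all in families of 3: R = 2.0, z/√R = 1.386, level 16.6% (simulated 16.3%).
- SCA1 v SCA3, only 5 and 7 pairs: D = 1 + 10(0.5)/30 = 1.167 and 1 + 14(0.5)/40 = 1.175. R = (1.167/30 + 1.175/40)/(1/30 + 1/40) = 1.170, level 7.0% (simulated 6.9%).

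**Premanifest v early-stage.** Take 23 families, each with one early-stage and two premanifest members. The variance of a family's contrast is 1 + (1 + ρ)/2 − 2ρ = 1.5(1 − ρ), against 1.5 under independence, so R = 1 − ρ. At ρ = 0.2 the level is 2.8%, and at ρ = 0.4 it is 1.1% (simulated 3.1% and 1.4%).

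**Patient v spouse control.** With k pairs across two groups of 30, R = 1 − kρ/30.

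**Simulated actual levels (normal data, ordinary rank sum test)**

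| Contrast | Nominal | Few relatives | Nearly all carriers in families |
|---|---|---|---|
| SCA1 v controls | 2.5% | 2.4-2.9% (5 pairs, ρ 0.1-0.5) | 2.6-6.2% (families of 2-3, ρ 0.1-0.5) |
| SCA1 v SCA3 | 5% | 5.3-6.9% (5 and 7 pairs, ρ 0.1-0.5) | 6.0-16.3% (families of 2-3, ρ 0.1-0.5) |
| Premanifest v early-stage | 5% | 3.9-4.5% (6 trios, ρ 0.2-0.4) | 1.4-3.1% (23 trios, ρ 0.2-0.4) |
| SCA1 v controls with spouse pairs | 2.5% | 2.2% (5 pairs, ρ 0.1) | 0.8% (15 pairs, ρ 0.5) |

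Repeat runs differ by up to about 0.3 percentage points. The right-hand column is an extreme for the carriers: 23 trios use 23 × 3 = 69 of the 70 carriers. In its last row, half of the 30 controls would be spouses of SCA1 participants.

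**The case against.** The strongest objection is that the protocol never says relatives are enrolled together. Being at risk implies an affected relative, not an enrolled one, and carriers also arrive through newsletters, flyers and earlier studies. The one remark on families, that "there is great variability in onset ages between patients with the same CAG repeat, even within the same family", is background on age at onset and says nothing about recruitment. This stands, and it is why the point is conditional. A reader might infer that at-risk participants are relatives of enrolled patients, so that the p-values are wrong and the false-positive rate exceeds its nominal level. The protocol does not support that: with few related pairs the level hardly moves.

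Second, spouses are not blood relatives, their number is unknown, and a volunteer pool also supplies controls. Any correlation would come from shared age or environment and may be near zero. The resulting error is conservative and cannot create a false validation. This also stands.

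Third, handling of family clusters is often left to a statistical analysis plan, and enrolment is run by the U01 study under a separate central IRB, which may have a family rule. This stands only in part. Section 15.3 does not leave the test open; it names one that assumes independence.

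The fallback to cluster approaches might be read as covering the point. It applies only if the comparisons are inconclusive and, in context, means grouping subjects, not allowing for family membership.

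**Conclusion.** The point holds as a conditional one. The protocol fixes a test that needs independent subjects, in a setting where it expects spouse controls and does not exclude several members of one family. If relatives are enrolled, the ordinary test is too liberal within groups, most of all for SCA1 v SCA3, and too conservative across groups, chiefly for premanifest v early-stage. The spouse effect is probably small.

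The size cannot be determined from the protocol. It ranges from negligible, with a handful of pairs, to roughly a threefold excess for SCA1 v SCA3 (16.3% against 5%) if every carrier belongs to an enrolled family of three with correlation 0.5. All of these figures rest on assumed family sizes and correlations and on normally distributed markers. This is a cheap improvement to a stated method, not a demonstrated error in the results.

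**What to change.** Obtain a coded family or household identifier from the U01 team, which already does the DNA testing, and carry it in the analysis data set. Give a spouse control the code of the patient's household. Collect it at enrolment, because relatedness may be hard to recover later from de-identified data.

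In 15.3, replace the ordinary test by one that respects this code: a rank sum test for clustered data (Datta-Satten type), or a regression on the marker or its ranks with a family random effect or family-clustered robust errors. The method must allow one family to contribute to both groups. Add a sensitivity analysis with one member per family.

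The cost is one coded variable, a change of wording, and slightly less favourable p-values for some carrier contrasts. If few relatives enrol, the results will barely change.

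### Section 15.3 appears to pool SCA1 and SCA3 in an unstratified premanifest v early-stage rank test; stratifying by genotype would protect power at little cost (optional improvement)

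*Protocol*

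**What the plan says.** Section 15.3 first compares SCA1, SCA3 and controls, globally and in pairs. It then adds that "premanifest carriers and early-stage patients will be compared using Wilcoxon rank sum test", with no mention of genotype as a stratum. The next sentence reads "Within each SCA group, premanifest and manifest patients will be compared regarding the biomarkers at baseline and during follow-up".

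Section 15.2 sets the numbers at "30 (20 premanifest and 10 early-phase) subjects with the SCA1 mutation" and "40 (27 premanifest and 13 early-phase) subjects with the SCA3 mutation". It also gives as one reason for the larger SCA3 cohort that "the diffusion MRI abnormalities in our preliminary data (see section 2.2) were less pronounced in SCA3 than those in SCA1".

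Section 15.2 gives no power, effect size or alpha for the premanifest v early-stage contrast. Its alpha of 0.025 is set "to take into account the two comparisons of SCA1 and SCA3 versus controls, two-tailed test", which is a different comparison.

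**The concern.** The protocol never says outright that the first stage test merges the two genotypes. If it did not, however, that sentence would largely repeat the one after it, so pooling is the natural reading.

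A pooled rank test ranks all 70 carriers together. If SCA1 and SCA3 sit at different biomarker levels, that difference spreads the ranks and is counted as noise against the stage effect. The protocol gives reason to expect a difference. Besides the sentence in 15.2, section 2.2 reports widespread diffusion changes in SCA1 but changes confined to the peduncles in SCA3. Section 2.3 reports clear tissue loss in SCA1 carriers and only slight brainstem loss in SCA3 carriers.

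At stake is power for the stage contrast in a rare-disease cohort that is hard to enlarge. There is a second, conditional risk: the pooled test keeps its type I error only while the two genotypes have similar stage ratios.

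**Working it through.** **Plan's own figure.** There is none for this contrast, so nothing can be reproduced directly. The nearby VBM calculation is useful only as a yardstick. It uses "controls (mean = 0.018, SD = 0.019") and "SCA (mean = 0.016, SD = 0.0019"). With SD 0.0019 in both groups, a simulated Wilcoxon test gives 94.8%, close to the stated 95%; with the printed control SD of 0.019 it gives about 8%. On the 0.0019 scale the whole SCA–control difference is (0.018 − 0.016)/0.0019 = 1.05 SD.

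**Inputs from section 15.2.** SCA1 20 premanifest and 10 early; SCA3 27 and 13. Pooled: 47 v 23, N = 70.

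**Assumptions.** Normal data with SD 1 within each genotype and stage; two-sided alpha 0.05; stage effect and genotype shift varied. Simulations used 20,000 to 40,000 runs per scenario.

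**Step 1: confounding at the planned mix.** The SCA1 share is 20/47 = 0.426 among premanifest and 10/23 = 0.435 among early-stage subjects. A genotype shift of g SD therefore moves the stage difference by only 0.009 × g SD, which is negligible.

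**Step 2: the two tests.**
- Pooled: Z = (W − 23×71/2)/√(47×23×71/12).
- van Elteren: T = (W₁ − E₁)/31 + (W₃ − E₃)/41, with variance V₁/31² + V₃/41², where V₁ = 20×10×31/12 = 516.7 and V₃ = 27×13×41/12 = 1199.3.

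**Step 3: why the pooled test is conservative.** With SCA1 share 30/70, the total variance is 1 + (30/70)(40/70)g² = 1 + 0.245g². At g = 1 this is 1.245, SD 1.116. The test scales by this total, but the true noise has SD 1, so the effective critical value is 1.96 × 1.116 = 2.19 and type I error is about 2.9%. The simulation gives 2.7%.

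**Step 4: simulated results, equal stage effect in both genotypes.**

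| Genotype shift | Power at 0.6 SD, pooled v stratified | Power at 0.75 SD, pooled v stratified | Pooled type I error |
|---|---|---|---|
| 0 | about 62 v 61% | 80.5 v 80.0% | 4.8% |
| 0.5 SD | 59–60 v 61% | 78–80 v 80% | 4.2% |
| 1 SD | 51–53 v 61% | 72–75 v 80% | 2.7% |

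The stratified test stays at 4.7–4.9% type I error. In each range, the higher power belongs to SCA3 being the less abnormal genotype, which is the direction the protocol expects.

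**Step 5: unequal stage effects.** With 1.0 SD in SCA1, 0.5 SD in SCA3 and SCA3 less abnormal, pooled v stratified power is 76.0 v 75.2% at no shift, 72 v 75% at 0.5 SD and 64 v 75% at 1 SD.

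**Step 6: if accrual departs from the plan.** Take SCA1 at 15:15 and SCA3 unchanged. The SCA1 share becomes 15/28 = 0.536 among early-stage and 15/42 = 0.357 among premanifest subjects. A 1 SD shift then adds a spurious stage difference of 0.179 SD. The true standard error is √(1/28 + 1/42) = 0.244, and the test rejects beyond 1.96 × 1.116 × 0.244 = 0.534. The rejection probability under no stage effect is P(Z > (0.534 − 0.179)/0.244) + P(Z < −(0.534 + 0.179)/0.244), about 7.5%. Simulation gives 7.4%, against about 5% for the stratified test.

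**Step 7: cost of stratifying.** The effective sample n₁n₂/N is 47×23/70 = 15.44 pooled and 20×10/30 + 27×13/40 = 15.44 stratified, so almost nothing is lost at the planned mix. Simulated costs at no shift are 0 to 1 point (largest 55.3 v 54.2%, effects 1.0 and 0.25 SD). One further case, with those effects and SCA3 shifted 0.5 SD toward more abnormal, costs about 2 points (56.0 v 54.1%). At 15:15 the effective sample would be 16.28 stratified against 16.80 pooled, about 3% less.

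**The case against.** The strongest reply is that nothing here is wrong. The planned test is valid at the intended mix and, at worst, conservative. No stated figure is contradicted, and stratification could be settled in a statistical analysis plan that is not at hand. Most of this stands and sets the level of the point. It does not remove the point, because section 15.3 already names a specific test.

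A reader might infer that the plan ignores genotype. It does not: the next sentence plans the comparison within each genotype. Those tests do not fully replace a combined one, however. At 0.75 SD they have about 44% power (SCA1) and 55% (SCA3), against 80% for the stratified combined test.

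A reader might also infer a large loss, since at shifts of 1.5 to 2 SD the simulated gap is wide. The document does not support shifts of that size. Section 15.2 gives direction only. The preliminary diffusion data rest on 8–9 subjects per group, and the SCA1 patients there were clinically worse (SARA 9 ± 5 v 6 ± 3), so part of that contrast may be severity. Section 2.1 limits both genotypes here to SARA below 3 or 3–9. For the one VBM metric that is quantified, 1 SD would already nearly equal the whole disease effect of 1.05 SD. Other biomarkers may differ more, but no SCA1–SCA3 size is given for any of them.

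**Conclusion.** The point holds as an optional improvement. On the natural but inferred reading that the overall stage test pools genotypes, it loses nothing if SCA1 and SCA3 do not differ. With equal stage effects it loses about 0–2 points of power at a 0.5 SD shift and about 5–10 points at 1 SD. With a smaller stage effect in the less abnormal SCA3, the losses are about 3 and 11 points. Pooled type I error falls to about 3% at 1 SD. All of this rests on assumed shifts and stage effects, normal data and alpha 0.05.

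It would be tempting to call the comparison biased. At 33.3% v 32.5% early-stage it is not. Bias needs both a genotype shift and a departure from the planned ratios, as in the 15:15 example, and the protocol gives no sign that such a departure is expected.

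**What to change.** In section 15.3, state that the overall premanifest v early-stage comparison uses the van Elteren (stratified Wilcoxon) test with genotype as stratum, and keep the planned within-genotype comparisons. If no pooled test was intended, say so instead.

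This changes one phrase and needs no extra subjects or data. The price in power at the planned mix is the 0–1 point shown above if the genotypes do not differ, and about 2 points in the one very unequal case. In return, power and type I error no longer depend on the size of the genotype shift, and type I error no longer depends on accrual matching the planned stage ratios.
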